Potential participants will be approached and pre-screened. Those who meet pre-screening criteria will attend a Screening Visit (Visit 1), where the informed consent process will be conducted and study eligibility will be confirmed. Eligible participants will attend four additional visits over the course of the study – the Enrollment Visit (Visit 2), Month 1 Visit (Visit 3), Month 2 Visit (Visit 4), and Month 3 Visit (Visit 5). Participants will take one ART pill per day, for 90 days total, while using the TruTag system and app. The app will facilitate reminders and serve as a two-way text communication platform between participants and the study team. Simple reminders will be sent following detected nonadherence with the aim of improving ART adherence. Timeline followback discussions will be conducted at the Month 1, Month 2, and Month 3 Visits to understand the context of any detected nonadherence. Dried blood spots (DBS) will be conducted at the Screening Visit (Visit 1) and the Month 3 Visit (Visit 5). Qualitative exit interviews will be conducted at the Month 3 Visit (Visit 5).

4. Participant Selection.

Recruitment. Individuals will be recruited through social media, flyering, and community outreach events in partnership with HIV advocacy groups and organizations serving LGBT populations in the greater Boston area. We will coordinate recruitment efforts with the recruitment team at The Fenway Institute (TFI), a dedicated group that assist research teams with identifying and matching potential participants with ongoing research studies at Fenway Health. The data team at TFI additionally compiles and generates periodic reports using specific inclusion criteria to generate lists of potentially eligible patients interested in participating in research. We will utilize a HIPAA waiver to obtain these reports from the Fenway Health electronic health record, and, following the identification of potentially eligible individuals, will contact primary care providers (PCPs) via email to obtain clearance to contact their patients, as needed per Fenway Health policy. We will contact interested individuals to explain the study in more detail and conduct a brief pre-screening to confirm eligibility.

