Month 1 Visit (Visit 3): Participants will attend the Month 1 Visit (Visit 3) approximately 30 days after the Enrollment Visit (Visit 2). This visit can be conducted remotely via Zoom. During this visit, study staff will conduct a timeline followback discussion in order to better understand the context of any nonadherence events detected by the TruTag system during the prior 30 days. Participants will also receive a technology refresher training at this visit, if needed, around the operation of the TruTag system and app. Participants will return any unused pills from the prior 30 days, which will be counted by study staff. Participants will be dispensed an additional 30-day supply of pills for the second month of the study. We will then issue a ClinCard payment and schedule the Month 2 Visit (Visit 4).

Month 2 Visit (Visit 4): Participants will attend the Month 2 Visit (Visit 4) approximately 30 days after the Month 1 Visit (Visit 3). This visit can be conducted remotely via Zoom. During this visit, we will conduct a timeline followback discussion regarding any nonadherence detected by the TruTag system during the prior 30 days. Participant will return any unused pills from the prior 30 days, which will be counted by study staff. Participants will be dispensed a final 30-day supply of pills for the third month of the study. We will then issue a ClinCard payment and schedule the Month 3 Visit (Visit 5).

Month 3 Visit (Visit 5): Participants will attend the Month 3 Visit (Visit 5) approximately 30 days after the Month 2 Visit (Visit 4). This is the final study visit. During this visit, we will conduct a timeline followback discussion regarding any nonadherence detected by the TruTag system during the prior 30 days. Participant will return any unused pills from the prior 30 days, which will be counted by study staff. Participants will complete the System Usability Scale. We will administer a blood draw for DBS testing as a measure of ART adherence, to be compared to TruTag-detected adherence. A study team member trained in qualitative methods will then conduct a digitally recorded, semi-structured qualitative exit interview in order to gauge user experiences operating the TruTag system during the 90-day study period. Participants will delete the TruTag app from their phone. We will then issue the final ClinCard payment.

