Remuneration. Participants will be remunerated a total of \$275 via the ClinCard system, according to the following payment schedule, upon completion of all study visit procedures.

Study Visit	Compensation
Screening Visit (Visit 1)	\$40
Enrollment Visit (Visit 2)	\$40
Month 1 Visit (Visit 3)	\$65
Month 2 Visit (Visit 4)	\$65
Month 3 Visit (Visit 5)	\$65
Total	\$275

TruTag System. The TruTag system leverages a silica-based FDA generally regarded as safe (GRAS) microparticle that is incorporated into the coating of B/F/TAF. When light shines from a smartphone camera onto the coated drug, the reflected optical image is interpreted as B/F/TAF. A corresponding app records each scan as an adherence event and patients using the TruTag system are coached to scan their medication prior to ingesting it. Dissolution of B/F/TAF when overcoated with the TruTag system was tested by Gilead Sciences, demonstrating that there is no change in dissolution. Specialty coated B/F/TAF will be provided through a cooperative agreement between Gilead Sciences and TruTag. In brief, B/F/TAF from the Gilead manufacturing supply chain will be overcoated with the TruTag system by ThermoFisher, the Gilead contract coating manufacturer. Drug will then be shipped in bottles of 30 to the Fenway Health Pharmacy.

In addition to recording adherence events, the TruTag app also provides a calendar for participants to review their adherence on-demand, as well as reminder systems that are triggered if no adherence event is detected by the TruTag system during a 24-hour period. Finally, the app

provides a secure platform to facilitate two-way text message communication between participants and the study team. This platform will be used to provide study-related reminders and communication in the setting of detected nonadherence.

In-Study Messaging. Participants will receive communications via the TruTag app during their participation in the study. Messaging will include: (1) daily adherence reminders, (2) reminders following detected nonadherence, (3) study-related reminders of upcoming visits, and (4) responses to technology-related questions.

Daily Adherence Reminders. During installation of the TruTag app, study staff will ask participants what time of day they expect to take their daily B/F/TAF dose. We will set up daily adherence reminders in the app for 10 minutes prior to their expected dosing period.

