Detected Nonadherence Reminders. The TruTag app will also be programmed to provide adherence reminders 60 minutes after the end of a dosing period, in the event that no ingestion has been detected. Additionally, if 48 hours of nonadherence is detected (i.e., 2 days of missed ingestions), study staff will utilize the two-way texting in the app to check in with participants. If participants do not respond to these nonadherence reminders, the study team will call or message participants to ensure that recorded nonadherence is not related to technological issues (i.e., related to operation of the TruTag system).

Study-Related Reminders. The TruTag app will be programmed to send reminders to participants in advance of each upcoming study visit. Reminders will be sent at 48 and 24 hours prior to the scheduled visit date.

Technology-Related Questions. We will encourage participants to report any technologyrelated questions and/or challenges to the study team via the TruTag app. We anticipate that these may include questions about how to operate the TruTag app, scan medication, or possible updates or reinstallations of the app. We will attempt to address technology-related issues through in-app messaging. If unsuccessful, we will contact participants by phone to troubleshoot technological concerns. if further assistance is required, we will schedule a study visit to assist participants with technology-related issues.

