Data Collection. Quantitative data will be collected via the baseline quantitative assessment at the Enrollment Visit (Visit 2), and via the System Usability Scale at the Month 3 Visit (Visit 5). Study staff will collect participant monthly adherence via the TruTag application and create timeline followback discussions at the Month 1 Visit (Visit 3), Month 2 Visit (Visit 4), and Month 3 Visit (Visit 5) to identify and contextualize adherence events of interest across the study period. Qualitative data will be collected via individual qualitative interviews at the Month 3 Visit (Visit 5). Dried blood spot testing will be conducted at the Screening Visit (Visit 1) and the Month 3 Visit (Visit 5). Lastly, general participant TruTag application usage will be collected to better understand participant engagement with the application. This will include: app engagement, including time spent in the app and which screens of the application participants access along with the frequency and time in which they spend on each screen on the application, as well as reminder data, including number of reminders delivered, timing of reminders, dosing window around which reminders will be sent, and conversion rate (days in which a reminder is delivered and adherence event recorded afterwards in the TruTag appl.

Baseline Quantitative Assessment. Quantitative data, including questions related to sociodemographics, use of ART, sexual history, mental health, attitudes about technology, medical mistrust, and substance use will be collected via a quantitative assessment. Quantitative data will be stored and managed on the REDCap platform hosted at TFI.

System Usability Scale. Participants will complete the System Usability Scale (SUS)¹¹ at the Month 3 Visit (Visit 5). The SUS is a 10-item Likert scale which will assess participants' perceptions of the usability of TruTag technology.

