Risks of Psychological Discomfort while Completing Assessments. Study questionnaires and interviews may include questions that individuals do not feel comfortable answering, or that may cause psychological discomfort. Individuals will be informed during the consent process that they may choose to skip any questions that they do not want to answer. They will also be reminded that they may withdraw from the study at any time, for any reason, without penalty.

Risks of Blood Draws. Participants will be informed during the consent process that they may have a bruise or pain from the site where blood samples are drawn. There is also a small risk of infection, lightheadedness, and/or fainting. To mitigate this risk, all study staff will be trained in phlebotomy at Fenway Health. We will ask participants who have a history of vasovagal syncope from blood draws to lie flat or sit in a recliner prior to blood draw. We will also have oral fluids available for participants at visits where blood draws are required.

8. Benefits.

Individuals may not benefit directly from participation in this study. They may indirectly benefit from learning about the TruTag system as a tool for measuring their ART adherence behaviors.

9. Statistical Analysis.

We will calculate basic descriptive statistics for key demographic variables. SUS scores will be summed and a mean score will be calculated for each participant. Overall SUS will be measured at each month during study participation. We will measure adherence via three strategies: (1) TruTag recorded adherence, (2) pill count at each monthly study visit, and (3) dried blood spot tenofovir alafenamide concentration. Correlation coefficients will be calculated between each of these adherence metrics. To measure if correlation of measures degrades over time (e.g., if individuals disengage from the TruTag system and stop using it over time), we will use a point biserial correlation.

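### Beyond the observed first dose, the plan has no day-level check for doses scanned but not taken, and its aggregate comparisons can show them only in part

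*Combined protocol and SAP*

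**What the plan says.** Section 6 (TruTag System) defines what is measured: "A corresponding app records each scan as an adherence event and patients using the TruTag system are coached to scan their medication prior to ingesting" the pill. The recorded event is therefore a scan that precedes the swallow. Section 6 (Detected Nonadherence Reminders) nonetheless equates a missing scan with a missing dose: the app prompts the participant "60 minutes after the end of a dosing period, in the event that no ingestion has been detected".

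The timeline followback starts from missing scans. Section 3 gives its purpose as "to understand the context of any detected nonadherence". At Month 1 the aim is to "conduct a timeline followback discussion in order to better understand the context of any nonadherence events detected by the TruTag system during the prior 30", counted in days; for Months 2 and 3 the text is "we will conduct a timeline followback discussion regarding any nonadherence detected by the TruTag system during the prior 30 days". Section 6 (Data Collection) is looser, "to identify and contextualize adherence events of interest across the study period", but does not define those events or say that scanned days are reviewed.

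Between visits, staff text a participant after 48 hours without a recorded dose. If there is no reply, "the study team will call or message participants to ensure that recorded nonadherence is not related to technological issues". This too follows only missing scans.

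Two measures do not depend on what TruTag detects: a count of returned pills at each monthly visit, and a dried blood spot at Month 3. The other blood spot is taken at Screening, before TruTag is used. On analysis, Section 9 says: "Correlation coefficients will be calculated between each of these adherence metrics". Its check for drift over time is a further correlation, and no other measure of agreement is planned.

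**The concern.** A scan-based record can be wrong in two ways: a dose taken without a scan, or a scan without a dose. The followback and the staff contacts can uncover the first. Neither is directed at the second, because neither opens a discussion of a day that carries a scan. The observed dose at Enrollment is the only scanned day on which the plan confirms ingestion directly.

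The secondary outcome compares TruTag with other adherence measures. For a system meant to measure adherence, recorded doses that were not taken are an important failure. As planned, the trial could report a high correlation and say little about how often that happens.

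**Working it through.** The documents state no error rate, power or precision figure to reproduce. The check is what each planned measure can reveal.

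**Inputs.** 30 pills per month, one per day (Section 6, Enrollment Visit); N = 15 (Section 2). All error counts and r values below are assumed for illustration.

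**Notation for one 30-day month.** a = days scanned and taken; b = taken, not scanned; c = scanned, not taken; d = neither; w = scanned-but-untaken pills that are discarded rather than returned (0 ≤ w ≤ c). Other untaken pills are assumed returned.

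- Scans: S = a + c
- Doses taken: T = a + b
- Pills used by count: P = a + b + w
- Signed difference: S − P = c − b − w
- Misclassified days: b + c
- Days the followback reaches as written in Section 3 and the visit descriptions: b + d, and none of the c days

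| Illustration | a, b, c, d | w | TruTag | Pill count | True | S − P | Days wrong |
|---|---|---|---|---|---|---|---|
| Over-scanning, pills returned | 27, 0, 3, 0 | 0 | 30/30 = 100% | 27/30 = 90% | 90% | +3 | 3 |
| Over-scanning, pills discarded | 27, 0, 3, 0 | 3 | 100% | 30/30 = 100% | 90% | 0 | 3 |
| Offsetting errors, pills returned | 24, 3, 3, 0 | 0 | 27/30 = 90% | 27/30 = 90% | 90% | 0 | 6/30 = 20% |

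Row 1: the count shows the over-recording as a monthly total. With 1 or 6 such pills in place of 3, it would read 29/30 = 96.7% or 24/30 = 80.0% against TruTag's 100%.

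Row 2: the count is blind, and only the blood spot could show the gap. It gives one on-study value per participant, not a value per day.

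Row 3: the totals agree although 6 days are wrong. The blood spot does not resolve this by number of doses, since 27 really were swallowed. The followback reaches the 3 unscanned days and 0 of the 3 scanned-but-untaken days.

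**What a correlation shows.** If TruTag over-records every participant by 2 pills a month (2/30 = 6.7 percentage points) and is otherwise exact, then y = x + 2/30. Deviations from the mean are unchanged, so r = 1.0; a numerical check with 15 simulated participants agrees. The signed difference would be +2 for each participant if the pills are returned.

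**Precision.** The Fisher-z 95% interval at N = 15, one pair per participant, is tanh(atanh r ± 1.96/√12). For r = 0.5 it is −0.02 to 0.81; for r = 0.7 it is 0.29 to 0.89.

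**The case against.** The strongest reply is that the plan does check TruTag from outside. Pill counts and the Month 3 blood spot can disagree with it in either direction, and Row 1 shows over-recording becoming visible. This stands. A reader might infer that a scanned-but-untaken dose can never come to light, or that the trial checks TruTag's errors in one direction only; the documents support neither. The gap is at day level, and the aggregate checks have limits: discarded pills, offsetting errors, and a single on-study blood spot. Months 1 and 2 may also be held by Zoom, with no stated method for returning and counting pills remotely.

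A reader might also infer that the 60-minute reminder breeds false records, because someone who swallowed without scanning could then scan another pill. On that day the dose was taken, so the adherent label is correct. The documents do not show this as a source of false adherence.

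It is also fair to say that the followback is meant to give context and is not one of the three adherence metrics in Section 9, that Row 3 needs exactly equal errors, and that even there the monthly total is right. All of this limits the size of the point. It does not supply a review of scanned days. The broader wording in Data Collection does not do so either, because its events are undefined and it sits uneasily with Section 3 and the visit descriptions.

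**Conclusion.** The point holds as a gap in day-level verification. After the observed first dose, no stated procedure asks about a scanned day. Doses scanned but not taken can appear only as a net discrepancy in the pill count or through the Month 3 blood spot, and the planned correlations report neither the size nor the direction of that discrepancy.

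How often such doses will occur cannot be judged from the documents. The 3-and-3 month illustrates what totals can hide and is not an estimate. The conclusion rests on reading the followback as Section 3 and the visit descriptions state it, and on a scan being logged whether or not the pill is then swallowed. The consequence is moderate: the primary outcomes are feasibility and acceptability in 15 people, and the adherence comparison is secondary. The change is worth making because it is cheap and improves that comparison.

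**What to change.** 1. At Months 1, 2 and 3, have the followback cover every day of the preceding 30, scanned days included. Take the participant's own account before staff go through the TruTag record with them. Reconcile the Data Collection wording with Section 3 and the visit descriptions.
2. Code each day as scanned and taken; taken, not scanned; scanned, not taken; or neither. Leave the raw TruTag record unaltered.
3. In Section 9, report the share of scanned days not taken and the share of unscanned days taken, both labelled as self-report.
4. Alongside the correlations, report scans minus pills used per participant-month, with its sign. State how pills are returned and counted when a visit is remote.

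The cost is a few more minutes at three existing visits, one coding form and some descriptive summaries; no extra visit, sample or participant is needed. The main downside is that 30-day recall is imperfect and not fully independent of TruTag, because participants can open the app's adherence calendar whenever they wish. The two shares should therefore be read as descriptive, not as validated error rates. The signed difference does not rely on recall, but it remains a net figure and is still blind to discarded pills and offsetting errors.

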Pre-screening. All interested individuals will undergo a pre-screening process, conducted via phone or in-person by a study RA, student intern, or other trained study team member, to evaluate preliminary eligibility. A Pre-Screen ID number will be assigned to each individual during this process. Data collected during pre-screening will be recorded in a password-protected spreadsheet or within REDCap hosted at TFI.

Informed Consent. Individuals who meet pre-screening criteria will be scheduled for a Screening Visit (Visit 1), where we will conduct the informed consent discussion and obtain written consent. A trained study RA will review the consent form with the individual in detail, discuss the overall goals of the study, and review all procedures. Individuals will be asked to voice their understanding of the information and will have adequate time to ask questions. If they agree to participate, they will be asked to sign the informed consent form and will be provided with a copy for their records. Informed consent discussions will take place in private consult rooms at TFI.

Inclusion Criteria		Exclusion Criteria	
1)	Age 18 or older	1)	Not English-speaking
2)	Living with HIV	2)	Unwilling to interact with the TruTag app
3)	Currently prescribed and taking Biktarvy as ART for at least 3 months		
4)	Undetectable viral load in prior 6 months		
5)	Owns iPhone model 11 or higher (non-SE only)		

5. Participant Enrollment.

Once the informed consent form and Medical Release Form have been signed, study staff will confirm eligibility. Individuals will be asked to provide their most recent viral load results to confirm undetectable viral load during the prior 6 months. If they do not have recent viral load results, study staff will obtain an HIV viral load during this visit, or, if preferred, individuals can obtain a viral load from their HIV care provider. Individuals who meet all criteria will be scheduled for an Enrollment Visit (Visit 2).

6. Study Procedures.

Study Visits. There are a total of five visits during the study period: the Screening Visit (Visit 1), Enrollment Visit (Visit 2), Month 1 Visit (Visit 3), Month 2 Visit (Visit 4), and Month 3 Visit (Visit 5).

[figure not shown]

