Screening Visit (Visit 1): As described above, potential participants will be approached and prescreened, either via phone or email, by a trained member of the study team. Individuals who meet the pre-screening criteria will be scheduled to attend an initial Screening Visit (Visit 1), where the informed consent process will be conducted and study eligibility will be confirmed. Following the consent process, individuals will be asked to sign a Medical Release Form and Locator Form. A Screen ID number will be assigned at this visit. Study staff will confirm that individuals have been diagnosed with HIV, have been taking Biktarvy for at least 3 months prior to the Screening Visit, and have an undetectable viral load documented within the past 6 months. Study staff will administer a blood draw for DBS testing, in order to measure baseline ART adherence. All individuals will be enrolled in the ClinCard remuneration system during this visit, and study staff will issue payment following completion of visit procedures. Following this visit, if eligibility has been confirmed, we will notify the Fenway Pharmacy and schedule participants for the Enrollment Visit (Visit 2).

Enrollment Visit (Visit 2): At the Enrollment Visit (Visit 2), participants will be formally enrolled in the study. Participants will complete a baseline quantitative assessment (e.g., sociodemographics, sexual history, attitudes about technology). Participants will be informed that they may skip any questions they do not feel comfortable answering. The study team will introduce participants to the TruTag technology via a brief PowerPoint presentation, which will cover its functionality and structure, and provide answers to common questions. Participants will receive a standardized training on operation of the TruTag system, and will be assisted with downloading the TruTag app onto their phone. We will assist participants in registering the app, and we will program in standardized reminders (see *In-Study Messaging* section). Study staff will bring a completed Prescription Card to the Fenway Pharmacy, which will dispense 30 ART pills for the first month of the study. Participants will be provided with the 30-day supply of pills and will be instructed to take one pill once daily. Their first dose will be observed by the study team during this visit. We will then issue a ClinCard payment and schedule the Month 1 Visit (Visit 3).

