Qualitative Interview. Qualitative data will be collected via individual, qualitative interviews. Interviews will follow a semi-structured guide, which contains key content areas, including overall perceptions of the TruTag technology, perspectives about this technology in the context of ART treatment, potential applications for the technology and associated adherence data, privacy and health-related concerns, and future recommendations. The interview guide will be semi-structured and will allow for interviews to be adapted based on participants' responses. Qualitative interviews will be conducted until thematic saturation is reached.

Study Outcomes. The primary outcomes will be the feasibility and acceptability of the TruTag system during the 90-day study period, which will be assessed through participant recruitment and engagement with the technology via adherence data, qualitative interviews at the end of the study, and quantitative assessments (i.e. SUS survey). We will additionally collect biological (HIV viral load) and pharmacologic (dried blood spot) data for a secondary outcome, which will be to correlate TruTag-recorded adherence with other traditional ART adherence measures.

Data Storage and Transfer. Secure Business Dropbox, hosted at Mass General Brigham (MGB), will be used for file storage in this study. Quantitative data will be stored and managed on the REDCap platform hosted at TFI. Quantitative assessments and qualitative interview transcripts will not be made publicly available. De-identified data may be shared with the study sponsor (TruTag). Audio files from qualitative interviews will be sent to Landmark Associates, Inc., a HIPAA-compliant external transcription company, via their online portal. Audio files will be removed from recording devices and from the Landmark portal when transcripts are available for download. Transcript files will be stored in access-protected folders behind the TFI firewall, accessible only to approved members of the study team. A secure Excel spreadsheet linking Study ID numbers to participants' names will be maintained in the same fashion.

7. Risks and Discomforts.

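### Does naming HIV viral load under the secondary outcome require an analysis that Section 9 does not give?

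*Combined protocol and SAP*

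**What the plan says.** Section 6, Study Outcomes, makes feasibility and acceptability primary, assessed through recruitment, engagement, exit interviews and the usability survey. It then adds: "We will additionally collect biological (HIV viral load) and pharmacologic (dried blood spot) data for a secondary outcome". The same sentence goes on to give the purpose of that outcome: "which will be to correlate TruTag-recorded adherence with other traditional ART adherence measures".

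Section 9 sets out the analysis: "We will measure adherence via three strategies: (1) TruTag recorded adherence, (2) pill count at each monthly study visit", with the last of the three being "3) dried blood spot tenofovir alafenamide concentration". The next sentence reads "Correlation coefficients will be calculated between each of these adherence metrics". Viral load does not appear in Section 9.

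Elsewhere in the readable text, viral load is an entry matter. The inclusion criteria in Section 4 require "Undetectable viral load in prior 6 months". Section 5 adds that a person without a recent result has one obtained by study staff at the Screening Visit or from their own HIV care provider. At that visit "individuals will be asked to sign a Medical Release Form and Locator Form". The Visit 1 blood spot is taken "in order to measure baseline ART adherence", and the Visit 5 blood spot is the one set against TruTag.

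**The concern.** Study Outcomes names two kinds of data for the correlation outcome, viral load and DBS. DBS has stated visits and a place in Section 9. Viral load has no place in Section 9, and the descriptions of Visits 2 to 5 and the Data Collection text do not schedule it. A reader could conclude that part of a secondary outcome has no planned analysis, so that any use of viral load would be chosen after the data were seen.

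There is also a practical worry. The obvious repair is to add viral load to the list of correlated measures, and in a sample of 15 people who are all suppressed at entry that correlation might not exist. If a sample during follow-up was intended, it would have to be arranged by Visit 5, the last visit.

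**Working it through.** The plan gives no figure to reproduce here: no power, alpha or target correlation is stated. The check sets the sections side by side and then asks what a viral-load analysis could yield.

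**1. What Section 9 needs.** Three measures give C(3,2) = 3 pairs. Their data sources are all described in Section 6: the TruTag app throughout, pill counts at Visits 3, 4 and 5, and DBS at Visits 1 and 5. Adding viral load would give C(4,2) = 6 pairs, of which 3 involve it. The existing 3 would not change.

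**2. What viral load the readable text supplies.** It supplies an entry value for each participant: a result from the previous 6 months or, failing that, one obtained at the Screening Visit or from the care provider. Section 6 counts the Screening Visit among the five visits of the study period, so viral load is not wholly without a time point. But this value precedes TruTag use. Coded as detectable or not, it is undetectable for all 15, its variance is 0, and a correlation coefficient has 0 in its denominator. A figure directly after the five-visit sentence is not shown in the copy read. It may schedule a later viral load, so the absence of one cannot be counted against the plan.

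**3. What a follow-up viral load could add.** The documents give no rate of detectable results, so a per-participant probability p is assumed, with N = 15 (Sections 2 and 3), independent participants, and viral load coded as detectable or not.

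- P(none detectable) = (1 − p)^15
- P(at most one) = (1 − p)^15 + 15p(1 − p)^14

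| Assumed p | None detectable | At most one |
|---|---|---|
| 1% | 0.860 | 0.990 |
| 2% | 0.739 | 0.965 |
| 5% | 0.463 | 0.829 |
| 10% | 0.206 | 0.549 |

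With none detectable, the coefficient is undefined.

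With exactly one, take TruTag adherence as untied ranks 1 to 15 (mean 8) and put the detectable participant at an extreme rank:

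- sum of cross-products = 15 − 8 = 7
- sum of squares of the ranks = 15 × (15² − 1)/12 = 280
- sum of squares of the indicator = 14/15
- largest |Spearman r| = 7/√(280 × 14/15) = 7/16.17 = 0.43

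There are 15 equally likely positions, so the smallest exact two-sided p-value is 2/15 = 0.13.

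**4. What each possible edit would change.** Deleting viral load from Study Outcomes changes no estimate. Writing in a time point and a descriptive summary adds a count of undetectable results among those measured, and possibly up to 15 assays. Neither touches the 3 planned correlations or the primary outcomes.

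**The case for a change.** The strongest case for a change is that this is a contradiction between two prose sections, which a missing figure cannot cure. Study Outcomes commits to collecting viral load for a named purpose, and Section 9 is a closed list that omits it. Even a small pilot should have its outcome and analysis sections agree, the repair costs one or two sentences, and silence leaves the handling of viral load to be settled after the data are in. The screening value cannot fill the gap. Results from medical records might be obtainable under the release form, but no section says they will be used.

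Most of this stands as description: the sections do differ, and the entry value cannot serve the correlation. What does not stand is the consequence. Section 9 is complete and workable for the measures it names. The room for choosing an analysis late is narrow, because a correlation would often be undefined or rest on one person, and the natural alternative is a count. The figures in step 3 depend on assumed rates and on a two-level coding that the plan does not specify. At 10% the correlation would more often be defined than not. They also test a correlation that Section 9 does not propose, so they show why little is lost, not that the plan is defective.

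**Conclusion.** No change to the plan follows. Viral load is named in Study Outcomes and absent from Section 9. This is a minor documentation mismatch, and analysts can fill it sensibly by running the three listed correlations and reporting any viral loads obtained as a count of undetectable results. The size of the effect on the planned results is nil: 3 of 3 Section 9 correlations and all primary outcomes are the same however the mention of viral load is read.

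This rests on Section 9 being followed as written, on the study being a single-group feasibility pilot of 15 people with no hypothesis test tied to viral load, and on everyone being undetectable at entry. It does not rest on any particular rate of detectable results during follow-up. The lack of a scheduled follow-up viral load is left open, because the figure in Section 6 was not available to check.
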